## IX. RESEARCH DESIGN AND METHODS

### Design

We will use a prospective, randomized, experimental design to accomplish the specific aims. Subjects (n=345) will be randomly assigned within 36 hours of intubation to one of three intervention groups which differ in frequency of tooth brushing (once, twice, or three times daily). The intervention, a standardized tooth brushing protocol developed and tested in the previous project, will be delivered by study personnel. Subjects will continue to receive scheduled interventions for the first 7 days of intubation, or until extubated if extubation occurs within 7 days; for subjects extubated within the intervention period, data collection will continue on days 1, 3, and 5 post-extubation. Dental plaque assessment, GCF for IL-1 $\beta$  determination, and data regarding HAIs and clinical status (for example, severity of illness) will be collected daily by study personnel who are blinded to group assignment.

All subjects will receive standard clinical care for mechanically ventilated patients, as per clinical guidelines and clinical agency guidelines. Standard clinical care includes all components of the IHI ventilator care bundle, including daily CHX. All subjects will receive oral comfort care by clinical providers at the provider's discretion. We will monitor reported compliance with the ventilator care bundle, and record characteristics and frequency of oral comfort care provided in order to assure that groups do not differ in usual clinical care.

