	Severity of Illness: APACHE	On study admission
	Global oral health: DMFT	On study admission

\*Post-extubation data will not be collected on subjects who remain intubated beyond the 7 day intervention period.

**Oral Health: Dental Plaque.** Dental plaque will be assessed using the University of Mississippi Oral Hygiene Index (UM-OHI), with observations documented and augmented by use of a digital intraoral camera (obtaining images of every tooth at each observation for later analysis). The UM-OHI assessed prior to the first tooth brushing intervention, and daily every day for the first seven days of intubation. If extubated during the 7 day intervention period of the study, the UM-OHI will also be assessed following extubation on days 1,3 and 5 post-extubation to document resolution or persistence of dental plaque after resumption of self-administered oral hygiene. We will use dental hygienists to train study personnel to obtain the digital images, and as plaque assessors.

The UM-OHI assesses every tooth, and divides each tooth into more sections than standard tools used in dental practice, thus enhancing the ability to quantify plaque. The UM-OHI divides the oral cavity into 12 regions: left and right posterior teeth and anterior teeth in each arch, further subdivided into buccal (cheek side) and lingual (tongue side). Each tooth is divided into 5 sections for the buccal surface and 5 sections for the lingual surface. The 5 sections include the mesial, distal and middle sections (which is further subdivided horizontally into gingival, middle and occlusal sections). Each section (total of 10 for each tooth) is scored for the presence or absence of plaque. If plaque definitely exists in the section, it is scored a 1; if no plaque is present, the section receives a 0. Thus, each tooth is scored from 0 (no plaque) to 10 (plaque in every section). The mean plaque score for the subject is then calculated by dividing the total score by number of teeth.

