**Serious Outcomes: SIRS, VAE and HAIs.** We will obtain data from the subject's medical record to evaluate SIRS criteria (heart rate > 90, respiratory rate > 20 or PaCO2 < 32 mm Hg, WBC > 12,000 mm^3 or < 4000 mm^3 or > 10% bands, temperature > 38 °C or < 36 °C) prior to the first tooth brushing intervention and daily thereafter while tooth brushing interventions continue. We will also monitor the results of any blood cultures obtained for clinical purposes from our subjects during the study period in order to identify clinical bacteremia. TGH has a robust surveillance program for

identification of bacteremia, VAC (including VAP), and sepsis. We will obtain HAI surveillance data regarding all study subjects from the Hospital Epidemiologist, as well as collecting data from each subject's medical record regarding diagnoses of these conditions by the clinical providers. We will also calculate length of intubation and length of stay for all subjects.

Sample Description and Patient Factors. Data will be collected from the medical record on additional factors in order to provide a comprehensive description of the study sample and conduct an exploration of the influence of individual-level factors on tooth brushing benefit and risk. Demographic data will be collected on study admission, and include age, gender, race, ethnicity, and smoking status. Preexisting global oral health will be measured by DMFT (Decayed, Missing, and Filled Tooth) Index assessed at study admission. The DMFT is a classic instrument which is widely used in dental practice and research. The score is calculated by visually inspecting each tooth and adding the number of decayed teeth, absent teeth, and filled teeth. Scores can range from a score of 0 (all teeth present and without caries) to a score of 32 (every tooth evidencing dental disease through loss, active dental caries, or repaired dental disease). The summative score will be used in examination of the exploratory aim. Severity of illness will be documented on admission to the study using the Acute Physiology, Age, and Chronic Health Evaluation (APACHE III). The APACHE III total score may range from 0 to 299 and consists of the following sub-scores: vital sign/lab, pH/pCO2, neurological, age, and chronic health. Scoring is done using the worst values for the first ICU day.

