Specific Aim 2 is to quantify and compare the safety of three tooth brushing frequencies on serious adverse outcomes, including ventilator associated complications and clinically relevant healthcare-associated infections. For aim #2, a composite HAI endpoint will be constructed consisting of VAP, bacteremia, and sepsis. Since HAIs are anticipated to be rare events across the 3 tooth brushing regimens, no formal between-group statistical testing will be conducted. Instead, 95% confidence intervals will be calculated for the proportion of subjects with HAI in each treatment arm. In addition, using person days of observation (i.e. days since intubation), we will calculate incidence rates (IR) of HAI by treatment arm and then calculate the number needed to harm (NNH) using the single daily brushing regimen as the

reference group and the formulas:  $NNH_{21} = (1 / (IR_2 - IR_1))$  and  $NNH_{31} = (1 / (IR_3 - IR_1))$  where  $IR_n$  = observed incidence rate in each treatment arm. In the event that the formal test of non-inferiority fails for the single daily brushing regimen, we will define clinically-relevant “compromised” safety as an NNH of 100 per less. This would be interpreted as 100 individuals or less being treated with the multiple daily tooth brushing to develop an HAI that otherwise would not have occurred with the single daily brushing regimen.

Clinical recommendations defined *a priori* and developed from the analyses conducted for aims 1 and 2 will be developed as defined in Table 2.

Table 2. Application of study findings to tooth brushing frequency recommendations

Comparison Groups a	Non-Inferiority	NNH	Recommendation	Rationale
1 versus 3	Supported	N/A	1 time/day	1 time/day non-inferior and safe
1 versus 3	Not supported	$\geq 100$	3 times/day	1 time/day inferior, 3 times/day safe
1 versus 3	Not supported	$< 50$	1 time/day	1 time/day inferior, but 3 times/day safety concern
1 versus 3	Not supported	50 to 100	See 1 vs. 2	1 time/day inferior, but 3 times/day safety concern
1 versus 2 b	Supported	N/A	1 time/day	1 time/day non-inferior and safe
1 versus 2 b	Not supported	$\geq 100$	2 times/day	1 time/day inferior, 2 times/day safe
1 versus 2 b	Not supported	$< 100$	1 times/day	1 time/day inferior, but 2 times/day safety concern

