**Statistical Power and Sample Size Justification.** As described above, our primary aim is to evaluate whether a single daily tooth brushing regimen is clinically non-inferior (defined as an effect size of  $\leq 0.50$ ) to a regimen of brushing twice or 3 times daily. The test is considered one-sided as there is no known or postulated biological mechanism to expect a better clinical result (lower plaque score) with the once daily brushing regimen, while at the same time, no reason to expect a higher risk of serious adverse events with this regimen as compared to 3 times daily brushing. To be conservative, we assume that up to 40% of subjects enrolled will have missing data or not provide analyzable data due to intubation for less than 48 hours or less than 2 days follow-up measurement of dental plaque and mucosal inflammation after intubation; this is consistent with our previous and current projects. The non-inferiority trial is powered based on conventional guidelines of type I error rate ( $\alpha$ ) of 0.10 and 95% desired power, and specifying a 1-tailed tolerance limit for non-inferiority as an effect size of 0.50. With these conditions, a sample size of 69 subjects per group (i.e. testing group 1 versus 3) is required. This group size will also be sufficient if the non-inferiority test is not supported, and a secondary test of the 1 versus 2 times daily brushing regimens is necessary. For 3 groups, the required effective sample size is 207 (69 x 3 groups), which taking into account missing and non-usable outcome data results in a proposed total sample size of 345 subjects (i.e. 207 / 0.60). For specific aim #2, it is difficult to estimate the expected proportion of HAs to occur in the respective treatment arms, particularly given the recent change in Centers for Disease Control and Prevention (CDC) National Healthcare Safety Network (NHSN) surveillance definitions for ventilator associated complications, including VAP. If the proportion of subjects who experience HAI within one of the treatment groups ( $n=69$ ) is 0.05, the corresponding 95% confidence interval would be 0.01 to 0.13, indicating reasonable precision.

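### The number needed to harm is computed in person-days but read as individuals, so Table 2 understates harm by a factor of roughly the mean days observed

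*Combined protocol and SAP*

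**What the plan says.** Under Specific Aim 2 in section XI (Data Analysis Plan), the composite HAI endpoint is VAP, bacteremia and sepsis. The plan states: "using person days of observation (i.e. days since intubation), we will calculate incidence rates (IR) of HAI by treatment arm". It sets NNH21 = 1/(IR2 − IR1) and NNH31 = 1/(IR3 − IR1), where each IR is the rate observed in that arm. No multiplier or time window is attached.

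NNH comes into play conditionally: "In the event that the formal test of non-inferiority fails for the single daily brushing regimen", compromised safety means an NNH of 100 or less. The plan then gives the unit: "This would be interpreted as 100 individuals or less being treated with the multiple daily tooth brushing to develop an HAI" that once-daily brushing would have avoided.

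Table 2 turns this into recommendations. In the 1 versus 3 rows, if non-inferiority is not supported:

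- NNH of 100 or more leads to three times daily, with the rationale "1 time/day inferior, 3 times/day safe".
- NNH below 50 leads to once daily.
- NNH from 50 to 100 leads to the 1 versus 2 comparison, which has its own cut-off of 100.

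On follow-up, the Design section says "for subjects extubated within the intervention period, data collection will continue on days 1, 3, and 5 post-extubation". The footnote to Table 1 adds: "Post-extubation data will not be collected on subjects who remain intubated beyond the 7 day intervention period".

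**The concern.** The reciprocal of events per person-day is person-days per extra event. It becomes a number of people only after division by the days each person contributes, and the plan never does this. A cut-off meant as 100 people is therefore applied to 100 person-days, which a handful of patients accumulate within days.

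When non-inferiority is supported, Table 2 recommends once daily and ignores NNH. When it is not, NNH alone decides whether brushing more often counts as safe, and this is the only route to recommending two or three times daily. An inflated NNH in that branch can place a harm that meets the plan's own definition of compromised safety in the row labelled safe. The protocol says its earlier data showed a trend toward more VAP with brushing three times a day, so this is the harm the rule exists to catch.

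**Working it through.** **Inputs**

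- Rate base (person-days since intubation), NNH formula and cut-offs of 100 and 50: Aim 2 text and Table 2.
- Reference HAI risk p1 = 0.05: the sample size paragraph's illustration, which begins "If the proportion of subjects who experience HAI within one of the treatment groups" and uses n = 69. The plan gives no worked NNH, but its interval for this proportion reproduces: the exact 95% limits at 0.05 × 69 = 3.45 events are 0.012 and 0.131, which round to the stated 0.01 and 0.13.
- Mean days observed, T: not given, so a range is used. By the schedule, a subject extubated on day d (1 to 7) has a last visit on day d + 5, that is day 6 to 12, and a subject still intubated at day 7 stops there. T is shorter with early discharge, death or withdrawal, or if only ventilated days count.
- Constant hazard: assumption.

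**Step 1. Size of the unit error.** For rare events, plan NNH ≈ T × per-person NNH. In exact form, with p = 1 − exp(−IR × T):

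plan NNH = T / ln[(1 − p1)/(1 − p3)]

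A plan NNH of 100 therefore corresponds to a risk difference of 0.95 × (1 − exp(−T/100)).

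| T (days) | Risk difference | Risk in 3-times arm | Per-person NNH |
|---|---|---|---|
| 2 | 0.0188 | 6.9% | 53 |
| 3 | 0.0281 | 7.8% | 36 |
| 5 | 0.0463 | 9.6% | 22 |
| 7 | 0.0642 | 11.4% | 16 |
| 12 (bound) | 0.1074 | 15.7% | 9 |

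Read in individuals, the cut-off of 100 would be a difference of 1/100, that is 6% against 5%.

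**Step 2. When a harm crosses into the safe row.**

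- 5% versus 7% (per-person NNH 1/0.02 = 50): ln(0.95/0.93) = 0.02128, so plan NNH reaches 100 at T = 100 × 0.02128 = 2.1 days.
- 5% versus 10% (per-person NNH 1/0.05 = 20): ln(0.95/0.90) = 0.05407, so it reaches 100 at T = 5.4 days. Plan NNH is 55.5 at T = 3, 92.5 at T = 5, 111 at T = 6, 129.5 at T = 7 and 222 at T = 12.

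**Step 3. Observed results, true risks 5% versus 10%.** With n per arm and equal person-days, plan NNH = nT/(x3 − x1), where x is the number of subjects with HAI. It is 100 or more when the excess is positive but no greater than nT/100; a tie gives an infinite NNH and is counted with these. At n = 115 (345/3) the excess can be as large as 3 events at T = 3, 5 at T = 5, 8 at T = 7 and 11 at T = 10. On the per-person scale it can be at most 1.

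| Scale | Probability of NNH ≥ 100 or tie, 115 per arm |
|---|---|
| Plan, T = 3 | 23% |
| Plan, T = 5 | 42% |
| Plan, T = 7 | 70% |
| Plan, T = 10 | 87% |
| Per person | 8.5% |

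A further 5.6% of trials show fewer HAIs in the 3-times arm whichever scale is used, so the per-person figure is about 14% if these also count as missed. When person-time stops at the event (40,000 simulated trials), the plan-scale figures are 21%, 40%, 60% and 81%. At 69 per arm with equal person-days they are 29%, 42%, 54% and 74%.

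**Step 4. How often NNH is consulted.** With 69 per arm, SE = √(2/69) = 0.170 in effect-size units, and P(not supported) = 1 − Φ[(0.50 − d)/SE − z].

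| True plaque effect d | 95% CI rule (z = 1.96) | One-sided α = 0.10 (z = 1.28) |
|---|---|---|
| 0 | 16% | 5% |
| 0.25 | 69% | 43% |
| 0.50 | 97.5% | 90% |

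The first rule is the one in the Aim 1 text; the second is the one behind n = 69. Neither column allows for covariate adjustment.

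**The case against.** **The direction is inferred.** The plan never writes that the rate is per single person-day. Expressed per 100 or per 1,000 person-days, the formula would give smaller values and would generally overstate harm. This stands as a caveat, but no multiplier appears in the text, and with one the result would still not be individuals.

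**T is unknown, and 12 days is one subject's maximum.** A mean of 12 would need every subject to be extubated on day 7 and seen at every visit. This stands: the T = 12 figures are a bound. At T of 2 or 3, the 5% versus 10% example is not mislabelled at expected values, although 5% versus 7% already is by T = 3.

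**Correcting the unit does not make Table 2 reliable.** With identical 5% risk in both arms, a per-person NNH below 100 still appears in 32% of trials at 115 per arm and 42% at 69, because at these sizes the cut-off is about one event. This stands, but it is a separate limitation due to sampling noise and does not justify leaving the unit wrong.

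**The error rates depend on the denominator and the non-inferiority rule.** Both versions are shown above; they change the size, not the existence, of the error.

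**Reach is limited.** The primary non-inferiority test, the sample size and the per-arm HAI proportions with their intervals are unaffected. That is correct.

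**Conclusion.** The concern holds. The NNH formula and its stated interpretation are in different units, and nothing in the documents reconciles them. That conclusion does not depend on T. With rates per single person-day, harm is understated whenever mean observation exceeds about one day, by a factor slightly below T at a 5% reference risk (100/22 ≈ 4.6 at T = 5).

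The effect can change the recommendation. Assuming 5% HAI on once daily and constant hazard, 5% versus 7% is labelled safe beyond about 2.1 days of mean observation, and 5% versus 10% beyond about 5.4 days. The consequence is confined to the branch where non-inferiority is not supported. Because Table 2 fixes the recommendations in advance and that branch has no other safety input, this must be corrected before the data are analysed by arm; choosing the unit afterwards could choose the recommendation.

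**What to change.** Put NNH on a per-person scale over one stated window of W days before applying any cut-off. Follow-up is unequal, so the preferred route is to convert each arm's person-day rate to a risk, 1 − exp(−IR × W), and take the reciprocal of the risk difference. This assumes a constant hazard over W. A simpler version is 1/[W × (IR3 − IR1)], and likewise for 2 versus 1.

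The alternative is to use the per-arm HAI proportions already planned, provided HAI is ascertained over the same W for every subject. The planned surveillance source could support this: "We will obtain HAI surveillance data regarding all study subjects from the Hospital Epidemiologist".

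State W and the unit of the rate, and reconcile the Aim 2 text and Table 2 to that unit. The investigators should confirm that the cut-offs of 100 and 50 are meant for that window; no change to them is proposed here.

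Two clarifications would help. State that a difference of zero or less means no excess was observed and does not fall in the rows below 50 or below 100. Report the risk difference with its 95% confidence interval beside each NNH, so the imprecision is visible.

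The cost is a decision on W, revised analysis-plan wording and a minor programming change, with no new visits or samples.

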## Summary

Despite its prominent position in bedside care, there is little evidence to judge the benefits or associated risks of nurse-administered tooth brushing for mechanically ventilated adults, and the optimal frequency of tooth brushing in the critically ill has never been experimentally determined. This project will complete the examination of oral care interventions in mechanically ventilated adults with a randomized clinical trial of tooth brushing frequency (once, twice, or three times daily) focused on conclusively defining the benefit and risk of varied frequencies, and identification of moderating patient-level factors for risk and benefit. The project's overall goal is to determine optimal tooth brushing frequency for mechanically ventilated adults. Optimal tooth brushing frequency is important for control of dental plaque and reduction of oral inflammation; it is likely to improve patient comfort, improve efficiency of nursing care, and may reduce systemic sequelae related to oral inflammation. The primary aims of the proposed project are: 1) Evaluate the clinical equivalence (non-inferiority) of three tooth brushing frequencies on oral health (dental plaque and mucosal inflammation) in critically ill adults receiving mechanical ventilation; and 2) Quantify and compare the safety of three tooth brushing frequencies on serious adverse outcomes, including ventilator associated complications and clinically relevant HAIs. A secondary aim is to investigate patient factors that influence tooth brushing frequency benefit and risk in critically ill adults. These objectives will be accomplished using a prospective, randomized, experimental design. Subjects (n=345) will be randomly assigned within 24 hours of intubation to one of three intervention groups which differ in frequency of tooth brushing delivered by study personnel (once, twice, or three times daily). Dental plaque (UM-OHI score, with observations documented and augmented by use of a digital intraoral camera), mucosal inflammation (gingival crevicular fluid IL-1 $\beta$ ), and HAIs will be assessed daily during the intervention period. The data analysis will focus on providing definitive clinical practice guidance through joint evaluation of non-inferiority (comparison of dental plaque between groups by analysis of covariance) and quantification of number needed to harm. Repeated measures linear mixed models (treating dental plaque and mucosal inflammation as separate outcome variables) will provide insight as to specific patient-level factors that may modify the clinical effectiveness and safety profile associated with frequency of tooth brushing. Information about efficacy and safety of each frequency of tooth brushing will provide a clear recommendation for optimal tooth brushing frequency with direct translation to clinical practice.

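### HAI person-time starts at intubation, up to 36 hours before randomisation; this inflates the NNH modestly (about 1.07 to 1.30 fold) and matters only near a Table 2 cut-point

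*Combined protocol and SAP*

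**What the plan says.** Section XI (Data Analysis Plan, Specific Aim 2) sets the time origin: "using person days of observation (i.e. days since intubation), we will calculate incidence rates (IR) of HAI by treatment arm". The NNH for three-times-daily against once-daily brushing is then 1/(IR3 - IR1), and Table 2 applies cut-points of 50 and 100 to it. The NNH decides the recommendation only where once-daily brushing fails the non-inferiority test. No between-arm test of HAI is planned.

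Allocation comes later than intubation. Section IX (Design) says that subjects "will be randomly assigned within 36 hours of intubation to one of three intervention groups". The Summary in section VII gives a shorter limit: "Subjects (n=345) will be randomly assigned within 24 hours of intubation". These two limits need to be reconciled.

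The brushing period is also counted from intubation: "Subjects will continue to receive scheduled interventions for the first 7 days of intubation, or until extubated". For subjects extubated within that period, "data collection will continue on days 1, 3, and 5 post-extubation", and Table 1 lists HAI surveillance at those visits. Events come from hospital surveillance and the medical record: "We will obtain HAI surveillance data regarding all study subjects from the Hospital Epidemiologist". No section says when person-time ends, or whether an HAI arising between intubation and randomisation is counted.

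**The concern.** Time before allocation cannot carry an effect of the assigned regimen, yet it enters the denominator of every arm's rate. Had the plan used a rate ratio, an equal lead-in would largely cancel. The NNH is the reciprocal of a rate difference, so it takes the full scaling.

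When IR3 exceeds IR1 the effect has one direction: the NNH rises and more frequent brushing looks safer. Table 2 compares a point estimate with fixed cut-points, so a modest scaling can move a result from one row to another. At stake is a rule that the plan describes as set in advance and meant to guide bedside practice.

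**Working it through.** **Inputs**
- Clock start: intubation (section XI, Aim 2).
- Lag L from intubation to randomisation: at most 36 h = 1.5 days (section IX), or 24 h = 1.0 day (section VII, Summary). The typical lag is not given; I assume 18 h = 0.75 day as a middle value.
- Observation W, counted from intubation: 7 days for a subject still intubated at day 7; up to 7 + 5 = 12 days for one extubated at day 7; 1.5 + 5 = 6.5 days for one randomised at 36 h and extubated at once. These follow from the visit schedule. Actual follow-up is not given.
- HAI proportion 0.05 and n = 69 (section XI, sample size). Randomised per arm: 345/3 = 115. Proportions for three-times-daily brushing are assumed.

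**The plan's own figure.** The plan states no expected daily rate or NNH. Its only Aim 2 figure is the interval 0.01 to 0.13 for a proportion of 0.05 in 69 subjects. The exact (Clopper-Pearson) interval with 0.05 x 69 = 3.45 events is 0.012 to 0.131, which agrees.

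**Effect of the clock.** Let a be the expected HAIs per subject before randomisation (equal in all arms, since nothing has been allocated) and b_k those after it in arm k.
- Intubation clock: IR_k = (a + b_k)/W, so IR3 - IR1 = (b3 - b1)/W.
- Randomisation clock: IR3 - IR1 = (b3 - b1)/(W - L).
- NNH inflation = W/(W - L).

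The term a cancels in expectation, so the inflation does not depend on whether earlier HAIs are counted. Person-days are summed, so the mean lag is what matters; 36 h for every subject is a ceiling.

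| W (days) | L = 0.75 | L = 1.0 | L = 1.5 |
|---|---|---|---|
| 6.5 | 6.5/5.75 = 1.13 | 6.5/5.5 = 1.18 | 6.5/5 = 1.30 |
| 7 | 7/6.25 = 1.12 | 7/6 = 1.17 | 7/5.5 = 1.27 |
| 12 | 12/11.25 = 1.07 | 12/11 = 1.09 | 12/10.5 = 1.14 |

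**When a cut-point is crossed.** With W = 7, the NNH on the randomisation clock must already lie in 89.3 to 100 or 44.6 to 50 (L = 0.75), or in 78.6 to 100 or 39.3 to 50 (L = 1.5 for all).

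Illustration with once-daily HAI at 0.05 and W = 7, where NNH = (W - L)/(p3 - 0.05):

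| Assumed p3 | Intubation clock | L = 0.75 removed | L = 1.5 removed | Table 2 row changes? |
|---|---|---|---|---|
| 0.10 | 140 | 125 | 110 | No |
| 0.115 | 107.7 | 96.2 | 84.6 | Yes, at 100 |
| 0.15 | 70 | 62.5 | 55 | No |
| 0.17 | 58.3 | 52.1 | 45.8 | Only at L = 1.5 |
| 0.20 | 46.7 | 41.7 | 36.7 | No |

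**In whole events (W = 7).** The excess needed for NNH below 100 is person-days per arm divided by 100, rounded up. With 69 per arm: 483/100 gives 5, 431.25/100 gives 5, 379.5/100 gives 4 (L = 0, 0.75, 1.5). With 115 per arm: 9, 8 and 7.

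**Simulation.** Binomial events, W = 7, 69 or 115 per arm, once-daily 0.05, three-times-daily 0.05 to 0.20. The chance that the clock alone changes the Table 2 category is 0 to 18% at L = 0.75, and 2 to 40% if every subject has L = 1.5.

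**Scale against other errors**
- Sampling: with 3.45 events and 69 x 7 = 483 person-days per arm, the 95% half-width of the rate difference is 1.96 x sqrt(2 x 3.45)/483 = 0.0107 per day. NNH = 100 corresponds to 0.01 per day.
- Units: 0.05 against 0.10 gives 1/0.05 = 20 per individual but 7/0.05 = 140 in person-days, a factor of 7.

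**The case against.** The strongest reply is that the lag is balanced by randomisation and small beside other errors in the same calculation. Both parts are true. Balance means that no arm is favoured in its own rate, but it does not protect a reciprocal difference. Sampling error and the units problem are indeed larger: the plan reads its result as "This would be interpreted as 100 individuals or less being treated with the multiple daily tooth brushing", although the reciprocal of a person-day rate is in person-days. Neither justifies a clock that starts before allocation.

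Two stronger readings are tempting and are not supported.
- A reader might infer that every rate is diluted. That holds only if HAIs before randomisation are left out. The documents do not say; if they are counted, a rate need not fall. Only the expected difference is sure to shrink. The Sample paragraph also has no exclusion for pneumonia at intubation, which the previous project did exclude, so early events may add noise.
- A reader might take a short stay, such as 3 days after randomisation, and get factors of 3.75/3 = 1.25 to 4.5/3 = 1.50. Table 1 continues HAI surveillance to day 5 after extubation, so such short observation applies mainly to early death, withdrawal or loss. It would apply more widely only if person-time ended at extubation, which the plan does not state.

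**Conclusion.** The point holds in a limited form. HAI person-time begins before allocation, and this inflates the expected NNH by about 1.07 to 1.30 fold, with 1.12 for a 7-day window and an 18-hour mean lag. The upper figure is close to a ceiling, since it needs every subject randomised at 36 hours and extubated at once. The range assumes equal mean lag and follow-up across arms and observation of about 6.5 to 12 days from intubation.

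It would go too far to say that the clock is enough to move results across Table 2. A recommendation changes only if three conditions meet: non-inferiority is not supported, IR3 exceeds IR1, and the NNH already lies near 50 or 100. The 5% against 11.5% case (107.7 against 96.2) shows that this can happen; most of the other illustrated cases do not change row. The rule is still worth correcting, because the direction favours calling more frequent brushing safe and the change is cheap.

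**What to change.** In section XI, Aim 2, define person-days as time from randomisation to first HAI, death or end of surveillance, and count only HAIs with onset in that time. State when surveillance ends, both for subjects extubated within 7 days and for those still intubated at day 7. Reconcile the 24-hour and 36-hour randomisation limits.

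In the same edit, put the NNH on the per-individual scale that the 50 and 100 cut-points assume. One way is to take it from the per-arm HAI proportions that the plan already reports, counted over the same window. This removes the person-time denominator, but the window still needs a stated start and end.

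The cost is a few sentences in the plan and two explicit data items, randomisation date and time and HAI onset date. Neither is listed in Table 1 or the data collection procedures, although the envelope procedure and the surveillance reports should make them obtainable. No change to sample size or visits is needed. The edit should be made before HAI data are analysed by arm, since Table 2 is presented as an advance rule.
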